age will be used to determine how many calories are provided to each participant. While on the KD/SA diet, patients are limited to drink non-caloric drinks (water, diet soda, coffee and tea without milk or sugar). In addition to the diets, MRI/fMRI/MRS scans, genetic tests, self-report ratings, motor activity, sleeping behavior, NP testing and personality measures will be obtained in all participants. The first MRI session and the first NP testing will be performed within the first 2-6 days of admission. The MRI sessions will be repeated on a weekly basis (second and third week of hospitalization; the later corresponding to the last week of their inpatient stay) and the NP testing will be repeated during the third week of hospitalization. MRI scanning session and NP tests are described below and are for research purpose only.

During the inpatient period, participants will be periodically monitored for signs of withdrawal and evaluated for mood, sleep and alcohol cravings. Compliance with diet adherence (KD or SA) will be closely monitored during the hospital stay using daily urine tests.

After the final MRI sessions, the study diets are discontinued and the individual blind will be broken on a per subject basis. If KD is discontinued this will be done by slowly increasing the levels of carbohydrates to the diets of the SA group [68]. The levels of carbohydrates in the control group remains constant throughout the study, but patients are still blind to treatment group.

Participants will then be released at about 3-4 weeks from the Clinical Center and will have a 3 month follow up period under this protocol which is discussed below in section 4.d.12 *Follow-Up*.

1. Ketogenic Diet (KD) / Standard American (SA) Snacks and Shakes: Participants will be randomized to a meal plan of either a ketogenic diet (KD) or standard American (SA) diet at the time they sign the consent (day 1 or 2 of admission). For each meal at breakfast, lunch and dinner, the diets will consist of SA meal (carbohydrate rich) or KD meal depending on treatment randomization. Compliance tests are done daily with urine tests measuring ketone levels by an independent person (BSN RN) [69], results of which are retained. To ensure that the diet is double blind in both the outpatient and inpatient phases, solid snacks are always ketogenic and shakes are either KD or SA.

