2. **Randomization and blinding:** The study has a blinded and randomized design. A randomization code will be generated prior to recruiting and patient randomization will be assigned accordingly. Since we expect a larger dropout in the KD group, we pre-set the ratio of KD:SA participants as 3:2 in the randomization generation.* Nurses and research staff who do CIWA, craving ratings and other study procedures with patients will not have access to the randomization key. An independent person (BSN RN) will perform and analyze daily ketone testing and blood pricks and will have access to the key. The nutrition department also has access to the randomization key to prepare the diets, but patients' diets will be sent out without information on its contents.* This ratio will be set for the first 20 participants. After the enrollment of 20 participants, the ratio will be evaluated by an independent person (BSN RN) based on diet compliance during their 3 weeks inpatient stay as per questionnaire and urine screen. Results are shared with the PI who will modify the ratio if needed to aim for a 50% KD versus 50% SA study completion.
3. **Diet Compliance:** In addition to daily urine tests (described above in section 4.e.1) and blood pricks, a daily questionnaire on whether additional food was consumed and whether the participant was compliant will be assessed by an independent person (BSN RN). On each day, participants will be asked if they were compliant to the diet (i.e. the shakes and snacks provided), or if additional food was consumed. If yes, which food items and at what time. At that time, they will also be encouraged to be compliant with the diet. All participants will be motivated on a daily basis to be compliant to their diet by nutrition department staff. If after the first 3 days of diet initiation a participant (in either KD or SA) self-reports non-compliance to the diet for 4

days, the PI will be informed and participant will be withdrawn and excluded from further study participation.

Additionally, if after the first 5 days of diet initiation, a participant in the KD group has 3 urine tests that are negative for ketone bodies, this participant will also be removed from the study. In this case, the independent person who monitors daily urine testing, will inform study staff about the compliance breach and the patient will be removed from the study.

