fMRI data will be analyzed using standard software such as statistical parametric mapping (SPM) software, AFNI, FSL, and/or in-house routines. For a standard fMRI analysis, all image volumes will be pre-processed to correct for inter-scan movement, and realigned within and between scans. Each subject's EPI images will be co-registered with the subject's own T1 anatomical images for individual analysis or co-registered to a template, generated by the population under study or a standard template. These co-registered images will also be normalized to a standard EPI template such as the Montreal Neurological Institute (MNI) reference brain for potential group analysis. Statistical analyses will be performed using fixed effects (for individual data), conjunctions analysis (between and/or within subjects), and random effects model (for group analysis such as gender differences). The fMRI signal change produced by a task will be estimated relative to baseline activation, or in comparison with other task. Resting state or steady state scans will also be analyzed using standard or in-house software and network analysis might be performed. Statistical contrasts of activation maps may be analyzed with within-subjects t-statistics. The analysis may include single individual cases, a group of participants with similar characteristics, or a comparison between males and females. Region of interest or whole brain analysis will be based on functional or anatomical landmarks. Data may be combined with other modalities and behavioral results.

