MRI data will be processed using adequate software such as SPM8, Freesurfer, Tortoise or DTI studio, to obtain, for each subject, images of gray and white matter, diffusion or perfusion maps. Images will then be compared using standard statistical parametric mapping software such as SPM, FSL, or AFNI, or even other more advanced programs as available. The statistical program will generate a group-specific adjusted mean value and an associated adjusted error variance for each voxel or region of interest that will be derived. Statistical significance may be established based on multiple-comparison corrections, permutations or simulations, in accordance with the analysis method selected. Data may be combined with other modalities and behavioral results. Accounting for multiple non-independent comparisons inherent in the analyses, a voxel level corrected P value < 0.05 will be used as the final threshold for significance. However, in line with functional imaging literature, results will also be reported as significant at a statistical threshold of $P < 0.001$, uncorrected, when a priori hypotheses require.

MRS data will be processed using specialized software packages such as LCModel, jMRUI or in house routines. These will be used to calculate ratios, such as GABA/Cr, NAA/Cr and, NAA/Cho. Anatomical images may be used to identify the ROI. Data may be combined with other modalities and behavioral results.

In case of group differences in severity of addiction or age due to randomization, we will add these variables as covariates to the analyses.

Plasma ghrelin

Weekly plasma ghrelin (total and acyl-ghrelin) will be analyzed using standard lab procedures [94]. Ghrelin levels will be compared between KD and SA group, and associated with weekly alcohol craving scores in both groups. We expect ghrelin to decrease in the KD versus SA group, and to be associated with the expected decreases in alcohol craving in KD.

b. Power analysis

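### Each participant's blind is broken after the final MRI, during enrolment, and nothing keeps diet from those who exclude scans or choose the methods for the primary imaging outcomes

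*Combined protocol and SAP*

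**What the plan says.** - **Timing of the break.** Under the study timeline in 4.e, the diets stop after the final MRI sessions and "the individual blind will be broken on a per subject basis". Discharge follows. The paragraph adds "but patients are still blind to treatment group". No recipient of the code is named.
- **A conflicting statement.** Item 4.e.1 explains the snack and shake arrangement with "To ensure that the diet is double blind in both the outpatient and inpatient phases".
- **Who holds the key.** Item 4.e.2 gives it to the independent nurse who does the ketone testing, and "The nutrition department also has access to the randomization key to prepare the diets". It also says: "Nurses and research staff who do CIWA, craving ratings and other study procedures with patients will not have access to the randomization key".
- **Primary outcomes.** Section 9.a lists fMRI, MRS and structural MRI among the primary measures.
- **Imaging methods.** For fMRI, 10.a allows "statistical parametric mapping (SPM) software, AFNI, FSL, and/or in-house routines", and either region-based or whole-brain analysis. For structural images, significance may rest on any of several correction approaches, "in accordance with the analysis method selected". MRS may be processed in LCModel, jMRUI or in-house code.
- **Scan quality.** Sections 4.e.4 and 4.f let a session be repeated if its data are unusable. Neither gives a motion or quality threshold, or says that the decision is made without knowledge of diet.

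**The concern.** The scheduled scans are acquired before the participant's code is opened, so the exposure lies in what happens to them afterwards: processing, exclusion and choice of method. If the people taking those decisions know the diet, a borderline scan can be kept or dropped, and a package, region mask or correction method preferred, in the light of which arm benefits. Blind patients and blind bedside raters do not protect against this. Imaging makes up much of the primary outcome set, so a diet effect created at this stage would be reported as a main result of the trial.

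**Working it through.** The plan states no figure on this point, so the check is mainly a comparison of its own statements.

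**1. When codes open.** The break is per participant, after the final MRI, with discharge at about 3–4 weeks. Section 10.b plans 100 recruited for 50 completers. If completers' final scans fall on different dates, 50 − 1 = 49 of the 50 codes are open before the last completer's final scan. Codes therefore open during enrolment and long before any analysis lock.

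**2. Who learns them.** Patients remain blind. The nutrition department and the independent nurse already hold the key. For the sentence to have any effect, someone else on the study side must learn the diet. The text does not say whether that means ward nurses, treating clinicians, the PI or imaging analysts.

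**3. Whether the two blinding statements fit.** The outpatient phase begins after discharge, and the code is broken before discharge. A double blind in the outpatient phase cannot stand beside that unless the break reaches nobody new.

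**4. Whether another rule shields the images.** The restriction in 4.e.2 covers people who work with patients. It does not mention image processing, quality decisions or method choice, and it says nothing about the period after the per-participant break. No section requires processing under code or a locked imaging plan before codes open.

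**5. Other routes to the diet.** The removal rule in 4.e.3 for repeated ketone-negative urine tests applies only to the ketogenic arm, and the monitor "will inform study staff about the compliance breach". A removal recognised as falling under that rule identifies the arm. Under 4.e.3 such a participant's first-week MRI still enters the analysis. Section 4.f also allows a return at a later date to repeat an MRI, which could fall after the break.

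**6. Scale of the open pipeline (illustration only).** Assumptions, not document figures: k variants of one comparison, each tested at two-sided 0.05, no diet effect, and equal correlation ρ between test statistics. Six variants corresponds to three named fMRI packages × region-based or whole-brain = 6. Model: Z_j = √ρ·C + √(1−ρ)·E_j, with C and E_j independent standard normal. The result is P(max|Z_j| > 1.96), from 400,000 draws.

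| k | ρ = 0.5 | ρ = 0.7 | ρ = 0.9 |
|---|---|---|---|
| 3 | 0.125 | 0.109 | 0.083 |
| 6 | 0.208 | 0.164 | 0.108 |

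For independent variants the formula is 1 − 0.95^k, giving 0.143 for k = 3 and 0.265 for k = 6. A single pipeline fixed in advance keeps 0.05.

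This calculation needs only that labels are known when the variant is chosen. Opening every code on the last day with the pipeline still open gives the same table. It therefore prices the open pipeline, not the early break. The simulated test is also simpler than the plan's image test, which uses a voxel-level corrected P < 0.05.

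**The case against.** The best defence is that the plan is less open than 10.a alone suggests.

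- Section 10.b states directional hypotheses (limbic cue response, saliency-network connectivity, prefrontal atrophy and ventricles) and mixed ANOVAs for the diet comparison.
- Section 10.a calls corrected P < 0.05 the final threshold and names only two conditional covariates, addiction severity and age.
- Section 4.e.4 fixes the MRS voxels, sequence and LC model.
- Section 21 sends coded MRS and fMRI data to two outside groups and matches results to subjects afterwards.
- Most repeat-scan decisions would precede the break.

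All of this stands as a partial limit, but gaps remain. The hypotheses come without masks, package or exclusion rules. An uncorrected P < 0.001 route is also allowed for a priori hypotheses. The covariate trigger, a group difference, has no criterion and can be judged only with arm labels. Section 10.a reopens the MRS software. Coded data are not necessarily free of a diet label, the associated data sent out are undefined, and structural MRI is not named in the transfers.

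Three stronger readings are tempting but unsupported:

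- **Imaging analysts are unblinded.** A reader might infer this from 4.e, but no section says that they, or the PI, receive codes at that point.
- **The early break costs 11–21% false positives.** It does not follow: that range arises from an open pipeline whenever labels are known. The part specific to early unblinding, scan exclusion with diet known, has no estimate.
- **The damage could not be undone.** Scans acquired blind can be re-checked under code and rerun through a fixed pipeline. That makes this more reparable than bias at data collection.

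**Conclusion.** The concern holds as a statement of what the plan permits. Codes open one participant at a time during enrolment, the recipient is unnamed, the blinding statements in 4.e conflict, and no rule keeps diet from the people who exclude scans or settle methods for the primary imaging outcomes. That someone on the study side is newly unblinded is an inference, though the only reading that gives the sentence effect. Whether imaging analysts are among them is unknown. The documents do not show that bias occurs and give no basis for sizing it. The change is worth making because it is cheap and protects primary outcomes, not because a distortion has been demonstrated.

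**What to change.** In 4.e:

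- Reconcile the per-participant code break with the double-blind outpatient statement.
- State that individual codes are not released to the PI, raters or imaging analysts until two things are done: the last participant's scans have passed quality control under code, and a dated imaging pipeline (package, region masks, exclusion criteria, covariates) is frozen.
- Leave the planned diet change to those who already hold the key, and keep emergency unblinding available.

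In section 21, state that data sent under both transfer agreements carry no diet label. If codes have already been opened under the present text, have those scans re-checked for quality by someone without access to diet, and run them through the frozen pipeline.

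The cost is a little extra documentation (the pipeline document and a quality-control record under code), and study staff wait until the end of the trial to learn individual diets. One limit remains: the MRS targets include acetone and β-hydroxybutyrate, so the spectra may reveal diet to the MRS analyst whatever the code rule. MRS exclusion criteria should therefore be fixed in advance.

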The first step for our screening is to obtain informed consent for 14-AA-0181 prior to any procedures being implemented. Subjects will undergo a comprehensive medical history and physical examination by a clinically credentialed licensed independent practitioner. The purpose of the medical history and examination is to rule out serious medical conditions that may be contraindications to protocol participation. A copy of the medical evaluation will be placed in the subjects NIH chart. Screening procedures will include: Demographics; vital signs including height, weight and temperature; standard laboratory tests (Chem Screen, CBC, and Urinalysis); STAT urine tests to identify drug abuse and NP testing; a urine pregnancy test for females who are able to become pregnant; and an EKG. We will also interview the subject to obtain a lifetime drug history (including but not limited to everything from caffeine, tobacco, alcohol, and common illicit drugs) and we will administer self-report questionnaires, which provide descriptive data necessary to our brain imaging program. Some of the self-report assessments will be administered to evaluate the inclusion of participants as well as to provide descriptive data in all of our subjects. It is possible that subjects could be excluded from the ketogenic diet study based on the information they provide to us. If on the 14-AA-0181 admission and screening day the subject agrees to participate, they are given the informed consent for the ketogenic diet study.

e. Study procedures

Study Timeline: After admission and initial 14-AA-0181 screening, AUD patients who agree to participate will first sign the consent for this study and then begin to undergo detoxification in the 1SE unit under 14-AA-0181. The current protocol will involve being randomized into one of two diets. One diet consists of a ketogenic diet (KD) snacks and shakes 3x p/day (high in fat). The other liquid diet consists of a standard American (SA) diet shakes 3x p/day in the proportions of carbohydrates, protein and fat of traditional western diet. SA will receive the same KD solid snacks, in order to keep the diets blind to participants. Both diets will be eucaloric such that a standard equation based on weight, height, sex and

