To measure the effectiveness of the ketogenic diet in increasing ketone bodies, we will measure ketones in urine daily as recommended for monitoring ketogenic diets in the management of epilepsy [70]. Specifically, we will measure acetoacetate (AA) in urine, in the early morning starting the day after initiation of the KD diet or the control diet and every day thereafter. We will use over-the-counter reagent strips (Ketostix, Bayer Vital GmbH, Leverkusen, Germany), which determine the presence of AA. Moreover,

beta-hydroxybutyrate (BHB) will be measured up to 5 times per week with a finger prick (Precision xtra, Abbott).

We will also measure beta-hydroxybutyrate and acetoacetate in blood at baseline and once each study week and free fatty acids once per week (no more than 8mL per week). These measures will be associated with MRS measures (e.g., correlate beta-hydroxybutyrate and acetoacetate in blood with β -hydroxybutyrate and acetone concentrations in the anterior cingulate and frontal white matter), and will provide information on potentially unwanted consequences of KD (e.g., potential disturbing effect of KD on free fatty acid concentrations). If the Laboratory of Medicine at the Clinical Center cannot provide quantitative measures for beta-hydroxybutyrate and acetoacetate, assays will be used from Wako Chemicals GmbH, Neuss, Germany). We will also measure plasma ghrelin (up to 6cc) at baseline and on a weekly basis.

Weekly blood draws are scheduled to monitor liver function (2.5 cc), platelet counts (2cc) and coagulation (INR, 3cc).

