- b. Ketogenic diet (KD): Ketogenic diets are not recommended in patients with urolithiasis, liver disorders, cardiomyopathy and chronic metabolic acidosis [67]. Despite being a controversial treatment, the ketogenic diet has been studied as a treatment aid for dyslipidemia, obesity diabetes, epilepsy, brain tumors, autism, and neuroprotection with positive results. We will exclude participants with a history of urolithiasis and liver disorders other than mild alcoholic hepatic changes to decrease the risk to the participants. Liver function will be monitored during the study on a weekly basis as it is standard during the detox and treatment of alcoholism. The diet will be discontinued if there is a progression of liver damage after the detox is completed (3-5 x the upper-bound limit). KD may also have potential side effects, including GI discomfort and constipation, dyslipidemia, and low platelet counts and coagulation problems. Platelet counts and coagulation will be monitored on a weekly basis and the diet will be discontinued if platelet count < 100,000 or INR > 1.5. Free fatty acid levels in blood will also be monitored on a weekly basis. To facilitate compliance and decrease the burden on the participants the diet will consist of a primarily liquid diet (house-made by Nutrition Department), in combination with ketogenic solid snacks (e.g., eggs, meat, fish, vegetables). The meals will be provided after an assessment with the nutritionist. Most of our treatment seeking alcohol dependent subjects have chronic problems with malnutrition and have a very poor intake of solids while they drink. Therefore, the liquid diet was considered a better option to improve compliance. An additional benefit is that it provides a way to make patients unaware of whether they are in the ketogenic- or control diet group. We will measure ketones on a weekly basis for diet compliance. If a subject is withdrawn from the study for non-compliance to the diet, he/she will be paid for procedures completed up to the point of withdrawal.
- c. Venous line placements: Subjects may have some discomfort and bruising from the needle insertion. Some people feel light-headed or faint. The risks of an

intravenous catheter also include bleeding, infection, or inflammation of the skin and vein with pain and swelling. These will be treated if they occur.

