NIH guidelines on conflict of interest have been distributed to all investigators.

b. Conflict of interest

There are no conflicts of interest to report.

c. Role of a commercial company or sponsor

There is no drug company involved.

21. Technology Transfer

This study now has two separate data transfer agreements (DTA's) in place under the following docket numbers:

1. AA DTA 22-11002: This DTA is between UPENN and NIAAA/LNI. We will send deidentified (coded) MRI imaging data for further analysis which includes: MRS and fMRI time series and associated data as well as craving data in response to alcohol cues from the fMRI scan sessions to our collaborator at UPENN for analyzation. UPENN will send back the results and we will match it back up to the subjects on our end.
2. AA DTA 22-11006: This DTA is between Zhejiang University, China, and NIAAA/LNI. We will send coded MRI imaging data for further analysis which includes: fMRI resting state time series and associated data as well as craving data in response to alcohol cues from the fMRI scan sessions to Zhejiang University China, for analysis. Zhejiang University will send back the results and we will match it back up to the subjects on our end.

22. Research and Travel Compensation

Volunteers will be compensated for time and research-related inconveniences, to the extent to which they complete them, as follows:

Procedures	Inconvenience Units	\$ Payment	Frequency	Total
Week 1 Study Procedures				
KD/SA Randomization Week	10	100	1	100
Genetics blood draw	1	10	1	10
Urine Drug Screen prior to MRI/NPT	1	10	1	10
Saliva Drug Screen prior to MRI/NPT	1	10	1	10
Urine pregnancy if female who can become pregnant prior to MRI/NPT	1	10	1	10
Ketone blood test #1 – obtained prior to start of KD/SA start	1	10	1	10
Ghrelin blood test #1 – obtained prior to start of KD/SA start	1	10	1	10
MRI session #1 (structure, functional reactivity, functional connectivity, MRS)	10	100	1	100
Neuropsychological Test Battery and Personality tests (NPT) including questionnaires Session #1	13	130	1	130

Sleep Profiler #1	10	100	1	100
Sleep Profiler #2	10	100	1	100
TMGENEActiv #1 (entire week of wear)	10	100	1	100
Ratings for Mood, Sleep, and Alcohol Craving	7	70	daily	total of 70
Daily urine ketone test	1	10	daily	total of 70
Ketone finger prick	1	10	Up to 5x/week	max of 50
Ketone blood test #2	1	10	1	10
Ghrelin blood test #2	1	10	1	10
Liver function, FFA platelets/coagulation blood test #1	1	10	1	10

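### Weekly fatty acid, platelet, INR and liver tests are taken in both diet arms, but no KD–SA comparison of them is planned and no pre-diet fatty acid value is listed

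*Combined protocol and SAP*

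**What the plan says.** **Purpose of the tests.** Section 4.e.1 takes beta-hydroxybutyrate and acetoacetate "in blood at baseline and once each study week and free fatty acids once per week (no more than 8mL per week". It gives two uses: "These measures will be associated with MRS measures", and they "will provide information on potentially unwanted consequences of KD", where the example is a disturbance of FFA. The same section adds: "Weekly blood draws are scheduled to monitor liver function (2.5 cc), platelet counts (2cc) and coagulation (INR, 3cc".

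**Named harms and limits.** Section 7.b states: "KD may also have potential side effects, including GI discomfort and constipation, dyslipidemia, and low platelet counts and coagulation problems". It ties platelets, INR and liver function to limits at which an individual's diet is discontinued, the liver limit applying only once detoxification is complete. FFA is to be monitored weekly, with no limit.

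**Schedule.** The table in Section 4.a and the list in Section 22 give both arms the same draws. Ketones and ghrelin are drawn twice in week 1, and Section 22 places the first draw before the diet starts. The entry "Liver function, FFA platelets/coagulation blood test #1" carries no such label.

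**Analysis.** Section 9 lists no laboratory or adverse-event outcome. In Section 10.a the only blood analyte compared by diet is ghrelin: "Ghrelin levels will be compared between KD and SA group".

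**Other safety provisions.** Section 8 grades adverse events by CTCAE v3.0. Section 14 has the principal investigator review each participant's safety data and look yearly for trends in adverse events and unanticipated problems. It does not say by arm and does not mention laboratory values.

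**The concern.** Section 4.e.1 states a purpose that no planned analysis serves. A per-patient limit protects that patient; it does not estimate what the diet does. Both arms are stopping alcohol at the same time, so a change over time in one arm cannot be credited to the diet. The randomised SA arm, with identical draws, is what would allow that, and the plan does not use it for these tests.

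Section 1 describes this as the first study of the diet in alcohol detoxification, so a pre-specified estimate of its effect on platelets, INR, liver tests and FFA would be of real use to whoever designs the next one. Most of the omission could be repaired later from data already held. The pre-diet FFA value could not: if the assay is not run, or serum not kept, that value is lost.

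**Working it through.** **1. Does the blood budget contain a pre-diet safety draw?** Inputs are the volumes in Section 4.e.1 and the totals in Section 7.d.

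- One safety draw (liver, platelets, INR): 2.5 + 2 + 3 = 7.5 cc.
- Three weekly draws: 3 × 7.5 = 22.5 cc, which reproduces the stated 23 cc. Four would be 30 cc. So no separate pre-diet safety draw is budgeted.
- Ghrelin: 4 × 6 = 24 cc, which reproduces the stated 24 cc and does include the pre-diet draw.

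**2. Which tests have a value before the diet?** Section 4.d lists, at screening under 14-AA-0181, "standard laboratory tests (Chem Screen, CBC, and Urinalysis". A CBC should supply platelets and a chemistry screen probably liver enzymes, though its contents are not itemised. Neither INR nor FFA is listed. When the week 1 FFA draw falls relative to diet start is not stated.

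**3. Is there room to run FFA on the pre-diet ketone sample?** Four draws at the 8 mL maximum are 4 × 8 = 32 mL, within the 48 cc that Section 7.d allots to FFA and ketones. The itemised total, 30 + 10 + 48 + 24 + 23 = 135 cc, stays below the 140 cc ceiling because nothing is drawn in addition. One condition is open: the 8 mL is a weekly maximum, week 1 already holds two ketone draws, and the assay volume is not given. A separate 7.5 cc pre-diet draw would be a different matter: 135 + 7.5 = 142.5 cc, above the ceiling.

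**4. Can limits stand in for a comparison?** The documents give no SDs or expected shifts for these tests, so this is an illustration in SD units. Assumptions: normal values, 25 per arm (the completer target), two-sided 5%, a diet shift of *d* SD towards the limit, and a limit *L* SD from the SA mean. The crossing probability is Φ(−L) on SA and Φ(−L + d) on KD. Power on means is two-sample noncentral *t*; power on crossings is a two-proportion normal approximation.

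| d | L | Expected crossings of 25, SA / KD | Chance of no KD crossing | Power, crossings | Power, means |
|---|---|---|---|---|---|
| 0.8 | 2 | 0.57 / 2.9 | 5% | 25% | 79% |
| 0.8 | 2.5 | 0.16 / 1.1 | 32% | 13% | 79% |
| 0.8 | 3 | 0.03 / 0.35 | 70% | 7% | 79% |
| 0.5 | 2 | 0.57 / 1.7 | 18% | 11% | 41% |
| 0.5 | 2.5 | 0.16 / 0.57 | 56% | 7% | 41% |
| 0.5 | 3 | 0.03 / 0.16 | 86% | 5% | 41% |

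At *d* = 0.33, power on means is 21%.

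**5. What could the comparison resolve?** At 25 v 25 and 80% power the detectable difference is 0.81 SD. Adjusting for a pre-diet value with correlation *r* multiplies this by √(1 − r²): 0.77, 0.70 and 0.58 SD at assumed *r* of 0.3, 0.5 and 0.7. The unadjusted 95% interval has half-width 2.01 × √(2/25) = 0.57 SD.

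**The case against.** The plan does not neglect these tests, and several stronger readings that a reader might infer are not supported.

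- *FFA is measured and then not used.* Section 4.e.1 also links these measures to MRS. What is absent is a limit and a safety analysis.
- *All the weekly tests are there because of diet harms.* Section 7.b describes weekly liver testing as usual practice in detoxification.
- *A harm would go unreported.* Adverse events are graded and trends reviewed yearly. Neither is stated to be by arm, so the supportable wording is that a moderate effect may be missed at group level.
- *The trial could not say what the diet does to these values.* Both arms have the draws, so the comparison remains possible; it is simply not pre-specified.
- *Without a baseline, FFA cannot be analysed.* Randomisation makes a post-baseline arm difference valid, and change from week 1 to week 3 can be computed. The missing value costs precision and the change from pre-diet.
- *Patients who reach a limit leave the later averages and flatter the diet.* Section 7.b says the diet stops; it does not say the blood draws stop.
- *Recovery from alcohol masks the harm.* This is plausible, but the documents give no recovery data for these tests.

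It can also be said that efficacy conclusions and sample size are untouched, and that a comparison this small misses moderate effects too. Both points stand, and they limit the weight of the concern. They do not supply the missing analysis.

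**Conclusion.** The omission is plain from the text. Section 4.e.1 promises information on unwanted effects of the diet, and no by-arm analysis of FFA, platelets, INR, liver tests or adverse events is pre-specified to deliver it. FFA, the measure named as the example, also lacks a limit and a listed pre-diet value.

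The size is moderate. On the assumed scale, a 0.8 SD shift is seen with 79% power in means against 7–25% in limit crossings; at 0.5 SD it is 41% against 5–11%. These figures rest on normality, 25 per arm and limits 2–3 SD from the SA mean, none of which is documented for these tests. They show that limits are a weak substitute for a comparison, not that harm is occurring or hidden. This is an inexpensive improvement worth making; the only part that cannot be recovered later is the pre-diet FFA.

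**What to change.** 1. **Pre-diet FFA.** Run FFA also on the pre-diet ketone blood sample #1, provided the assay fits the weekly 8 mL maximum in Section 4.e.1. The laboratory should confirm the volume first.
2. **Section 10.a.** Add a KD–SA comparison, by assigned diet, of weekly FFA, platelets, INR and liver tests (log scale) in everyone who started a diet, including any value that led to a stop. Report estimates with 95% intervals. Adjust platelets and liver tests for the screening CBC and Chem Screen where available, and FFA for the new pre-diet value. Compare INR unadjusted, since no admission INR is listed.
3. **Tables by arm.** Report limit crossings and CTCAE-graded adverse events by diet.

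Cost: one extra assay per patient on blood already drawn, one paragraph and a few tables. With intervals of roughly ±0.57 SD before adjustment, the text should say that a null result does not show safety. No change to any stopping limit is proposed.
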